### **3.2 MRI Data Acquisition**

MRI studies may be performed by both the Biomedical & Metabolic Imaging Branch (NIDDK) on a 3.0T Siemens Verio whole body instrument and/or the NMR Center on a GE 3T

scanner. A 70 cm tube resonator will be used for radio frequency transmission and detection. Padding will be used to minimize motion. Including clinical images to be read by radiology, MRI portion will take less than 120 minutes. The participant will be asked to provide a venous blood sample prior to MR imaging. Imaging may take place 3-5 hours after a standard meal, depending on facility availability.

We will be using the MRI for investigational research. This means that the way the MRI is generating the images may be different than what is normally done in a routine clinical scan. However, all studies done under this protocol will be performed within FDA safety guidelines. To collect images for research, we will use standard clinical coils (antennae). These are parts of the machine that help generate the image. Additionally, we will use clinical MR machines used within the FDA safety guidelines.

### **3.2.1 ANATOMICAL MRI**

Structural MR images will be obtained with a T1-weighted axial 3D modified driven equilibrium Fourier transform, and a T2-weighted coronal hyper-echo pulse sequences. This high-resolution scan will provide the basis for localizing courser-resolution PET data onto the participant's own anatomy. We will also obtain structural images using a magnetization transfer (MT) imaging that is based on the balanced steady-state free precession method (Gloor, Scheffler and Bieri, 2008). These images will be contrasted with T2-weighted data to determine white matter integrity.

### **3.2.2 FUNCTIONAL MRI**

fMRI will be collected depending on availability of facilities. Facility schedule permitting, the following fMRI data will be collected using a coronal single-shot gradient-echo echo-planar imaging (EPI) sequence.

*Neural bases of food stimulus perception.* To evaluate the neural bases of food stimulus perception, subjects may be presented with photographs of four different types of foods: high-fat savory foods, low-fat savory foods, high-fat sweet foods, and low-fat sweet foods. Presentation of the food stimuli will be blocked by food category. Each block will contain photographs of food stimuli from a given category, each presented for 2.5 seconds with a 500 ms interstimulus interval. In addition to food picture blocks, subjects will also be shown blocks of non-food object photographs that will serve as an object perception control condition. The participants' task while viewing the stimuli will be simply to press a button on a hand-held response box anytime they see the same picture presented twice in a row. Picture presentation blocks will be separated by 10-second 'null-stimulus' blocks in which only a small fixation mark will be presented on the screen. These null periods will be included to allow the blood oxygenation-related fMRI signal to return to baseline after each stimulus block. Each run will be completed three times, for a total duration of about 18 minutes.

By comparing the activity associated with viewing food- and non-food stimuli, we will localize in each subject the brain regions supporting food perception in general. In addition, by comparing activity among the four food stimulus categories, we will localize ROIs supporting perception of each food type. Finally, by comparing activity between obese and lean individuals, this research

design will also allow us to identify group differences in the perception of food stimuli in general, as well as among the four food stimulus categories.

*Relationship between dopamine D2 binding potential and activation in brain regions supporting food preference judgments.* To investigate the relationship between dopaminergic tone and neural responses to food stimuli and food preference, volunteers may perform an fMRI task in which they will provide preference ratings in response to photographs of high-fat savory foods, low-fat savory foods, high-fat sweet foods, and low-fat sweet foods. Food stimuli will be presented in a fast event-related design, with individual stimuli appearing in a pseudo-random order. Each stimulus will be presented for 5-seconds during which subjects will provide a rating to the following question:

*“if given the opportunity right now, how pleasant it would be to eat this food?”*

by manipulating a handheld MR-compatible scroll wheel to select a location on a number line. To allow mathematical deconvolution of the responses to stimulus presentations, each picture presentation will be followed by the appearance of a simple ‘null-stimulus’ fixation mark for between 2.5-7.5 seconds. In each run, 36 stimuli are presented (9 from each food category) for 5 seconds each. Each run, including instructions, stimuli and null periods, will last 4.5 minutes. Subjects will complete 4 runs of this task for a total duration of 18 minutes.

Analyses will include using subjects’ ratings on the “liking” question as covariates on the imaging data to identify brain regions supporting food preference judgments for each of the four classes of food stimuli [19]. In addition to addressing this using whole-brain imaging analyses, we will also explore how activity during food-preference judgments is modulated within the functionally-defined ROIs identified in the food perception functional localizer experiments described above.

*Functional connectivity among brain regions supporting gustation and perception of food stimuli.* Resting-state functional connectivity analyses will be used to examine connectivity between food perception areas and related regions. Volunteers will undergo two runs of an 8-minute “resting state” fMRI scan. During this scan subjects will be asked to stare at a fixation mark located in the center of the display, and to do their best to clear their minds and not think about anything in particular. Seed voxels for the resting-state connectivity analyses will be selected using data from food perception ROIs. Total duration for this portion is 16 minutes.

### **3.2.3 MAGNETIC RESONANCE SPECTROSCOPY**

Magnetic Resonance Spectroscopy (MRS) can quantify a variety of neurochemicals, including various neurotransmitters and their byproducts (e.g., glutamate, glutamine and GABA) and constituents of metabolic pathways (choline and creatine). MRS will be performed to assess neurometabolic profile of brain regions of interest. The MRS scan will last no more than 2 hours and poses no additional participant risk as gadolinium, a contrast agent sometimes administered to enhance visualization of the heart and blood vessels, will again not be used during MR study scans.

### **3.3 Metabolic Status and Endocrine Functioning**

In order to explore the metabolic and endocrine correlates of brain dopamine D2BP and neural bases of food perception and preference, participants will undergo periodic blood sampling and continuous glucose monitoring during the inpatient phase. Research blood sampling will be repeated during the 1-year follow up visit to the Clinical Center. Note that blood sample collected during screening visit will be for clinical purposes only to determine eligibility for study enrollment.

#### **3.3.1 RESTING ENERGY EXPENDITURE (METABOLIC CART)**

The measurement will be performed in the morning after a 12 h fast and overnight rest with the subject in a supine position. An indirect calorimeter with the ventilated hood technique will be used for the 30 min measurement (the first 5 minutes will be excluded from analysis). The respiratory quotient will be calculated as the ratio of carbon dioxide production to oxygen consumption. Resting energy expenditure will be calculated using the principles of indirect calorimetry using the  $\text{VO}_2$  and  $\text{VCO}_2$  measurements [20].

#### **3.3.2 BODY COMPOSITION MEASUREMENTS**

Assessments of body composition may be performed using the following procedures, depending on availability of equipment.

Dual Energy X-Ray Absorptiometry (DEXA) scans will be performed using the General Electric Lunar iDXA (General Electric; Milwaukee, WI, USA) to determine body composition. Participants will change into a hospital gown, remove all metal-containing objects and lie on a table while the scanner, which emits low energy X-rays, passes along the body. The scan will take approximately 10 minutes. The radiation dose is less than 0.001 rem, which is below the guideline of 5 rem per year allowed for research subjects by the NIH Radiation Safety Committee.

Assessment of body density will be obtained using an air displacement plethysmography chamber (BodPod). Subjects will be weighed and then evaluated in the chamber while clothed in a tight-fitting bathing suit or underwear and acrylic bathing cap. Final body volume will be calculated based on initial body volume corrected for the subject's thoracic gas volume as measured by the breathing circuit housed in the rear of the chamber through a disposable tube.

We will use bioelectrical impedance spectroscopy (BIS) to measure the impedance of the body. BIS spectra will be obtained to estimate total body water (TBW) and extracellular water (ECW), as tissue impedance at low frequencies is controlled by the electrical properties of ECW and at high frequencies by the electrical properties of TBW. Subjects are measured by two sets of electrodes placed on the hand/wrist and foot/ankle while lying supine on a nonconductive surface. This is a non-invasive test.

#### **3.3.3 PHYSICAL ACTIVITY MONITORING**

Subjects will be provided with commercial-grade accelerometers to measure physical activity and sleep patterns *daily* during both the outpatient portion (phase C), and daily over the course of 12 months until 1-year follow up visit (phase D).

### 3.3.4 BODY WEIGHT MONITORING

Subjects will be provided with a wireless scale for home use and asked to monitor body weight *daily* during both the outpatient portion (phase C), and daily over the course of 12 months until their 1-year follow-up visit (phase D).

### 3.3.5 DOUBLY LABELED WATER

Subjects will receive a dose of doubly labeled water at the end of their inpatient visit. We will collect a baseline (predose) urine sample after which subjects will then drink from a stock solution of a mixture of 10% enriched  $\text{H}_2^{18}\text{O}$  and 99% enriched  $^{2}\text{H}_2\text{O}$  followed by 100-200 mL tap water to rinse the dose container. Each DLW dose will be obtained from a larger DLW batch containing a mixture of  $2\text{H}_2\text{O}$  (99% enrichment) and  $\text{H}_2^{18}\text{O}$  (10% enrichment). The dose of DLW will be prepared individually for each subject (proposed dosage: 1 g DLW/kg of body weight). Spot urine samples will be collected immediately prior to dosing and at 1.5, 3, 4.5, and 6 hours after dosing and daily thereafter. Daily urine samples will be collected for 1-2 weeks after each dose has been administered in order to assess isotopic enrichments of urine samples as measured by isotope ratio mass spectrometry. The average  $\text{CO}_2$  production rate will be estimated from the differential disappearance of the two stable isotopes in the urine samples [21].

### 3.3.6 BLOOD SAMPLING FOR SUBSTRATE AND HORMONE CONCENTRATIONS

Blood samples will be collected into chilled test tubes containing sodium fluoride, EDTA, and aprotinin as preservatives. Those samples for which analysis of gastrointestinal peptides will take place will also contain a dipeptidyl peptidase IV inhibitor and a protease inhibitor (e.g., 4-(2-aminoethyl benzenesulfonyl fluoride) and be collected into chilled glass tubes. All samples will be kept on ice and then centrifuged (1600 g for 15 min at 4°C) within 30 min of collection for isolation of plasma. After centrifugation, the plasma will immediately be frozen and stored at -80°C for later analysis.

Example plasma substrate and hormone concentrations of interest are described in **Table 3**. The results of all bloodwork from the screening visit will be reviewed with and made available to the participant to provide to their personal physician as desired. Given data from in-patient procedures are acquired for research purposes and therefore have minimal clinical utility, results from in-patient tests will generally not be provided to participants. If any procedures of this protocol show clinically significant abnormalities that may impact the health and well-being of the subjects, however, they will be notified by a qualified member of the research team. Appropriate follow-up with their primary care physician will be planned. If needed, the research team will refer subjects to a health care provider.

**Table 3.** List of blood measurements (\*all measures plasma based except where noted)

	Metabolite/hormone
Metabolites	
	Triglycerides/LDL/HDL/Total cholesterol
	Fatty acids*(erythrocyte and plasma)
	Glucose
	Chemistry
	Homovanillic acid

Hormones	Insulin Glucagon Leptin C-peptide Epinephrine Adiponectin GLP-1 (active form) PYY 3-36 Acyl- and total ghrelin GIP FGF21 TSH Triiodothyronine (T3, f-T3) Thyroxine (T4, f-T4) FSH LH Testosterone (T, f-T) Estrogen Cortisol
Markers of Inflammation	CRP IL-6 TNF-alpha

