## **9. Research Use, Storage, and Disposition of Human Subjects' Samples and Data**

As with all clinical data, the findings from this study will be kept confidential to protect Personally Identifiable Information (PII). Volunteer clinical data will be protected and tracked using standard operating procedures in the medical record department. All research charts and records will be kept in a secure place in a locked file cabinet in the office of the Principal Investigator. All research samples and data will be identified by a study code linked to the subject's name and the code and the results of all analyses will be kept strictly confidential. All research samples (e.g., blood, fluids) will be coded for storage in refrigerators and freezers in a locked laboratory. The plan is to store the samples until they are analyzed, and a sample of serum will be safeguarded for future analysis of other factors related to obesity and its phenotypes. These samples will be stored indefinitely. The IRB will be notified in the event these samples are accidentally destroyed, lost or are anonymized. Studies on these samples will always be related to the scope of this proposal.

Some clinically relevant research data will be stored indefinitely in the subject's medical record. This data will be accessible to the subject for review by others of the participant's choosing

(doctors, insurance companies etc.) after completing a release of information. This and other data will be maintained in databases that are password protected and secure.

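### The only tube and handling described for the research bloods (fluoride/EDTA/aprotinin, spun to plasma) does not suit the Chemistry panel in Table 3, gives no source for the banked serum, and omits a red-cell storage step

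*Combined protocol and SAP*

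**What the plan says.** Section 3.3.6 sets the handling for research blood used for substrates and hormones.

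- **Tube:** "Blood samples will be collected into chilled test tubes containing sodium fluoride, EDTA, and aprotinin as preservatives".
- **Gut-peptide samples:** "Those samples for which analysis of gastrointestinal peptides will take place will also contain a dipeptidyl peptidase IV inhibitor", together with a protease inhibitor. These are additions to the same base, so the tubes remain anticoagulated.
- **Processing:** "All samples will be kept on ice and then centrifuged", and this is done "within 30 min of collection for isolation of plasma".
- **Storage:** "After centrifugation, the plasma will immediately be frozen and stored at -80°C for later analysis".

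Table 3, in the same section, is captioned as plasma based unless a measure is marked otherwise. Chemistry is listed without such a mark. The one marked exception is "Fatty acids*(erythrocyte and plasma").

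Section 9 adds a bank: "a sample of serum will be safeguarded for future analysis of other factors related to obesity and its phenotypes". These samples are to be kept indefinitely.

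Two other blood collections fall outside this route. Section 3.7 provides an additional 5 mL for DNA. Section 2.3.1 describes a routine screening panel that includes electrolytes and a liver panel, and section 3.3 says the screening blood is for clinical use only, to decide eligibility.

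**The concern.** A handling rule fixes what can be measured later. Followed as written, section 3.3.6 meets three difficulties.

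1. Chemistry would be measured in plasma that carries additives which are themselves analytes of a usual chemistry panel, or which bind or inhibit such analytes.
2. Serum is what remains after blood clots. EDTA prevents clotting, so the serum promised in section 9 has no described source.
3. Red-cell fatty acids are wanted, but the text says nothing about keeping the cells.

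The choice is made at the draw. Serum cannot be recovered from EDTA blood afterwards, and additive effects cannot be subtracted reliably when the concentrations are not recorded. The samples feed Exploratory Aim 2 (metabolic and endocrine correlates of D2 binding potential) and the future bank.

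**Working it through.** The plan states no figure on this point, so there is none to reproduce. The check sets the sections side by side; a short calculation then shows the possible size of the additive effect.

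**Step 1. What is promised against what is collected**

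| Promised | Where | Matrix needed | Provided by section 3.3.6? |
|---|---|---|---|
| Chemistry | Table 3, no exception | Plasma or serum free of interfering additives | Only fluoride/EDTA/aprotinin plasma is described |
| Erythrocyte fatty acids | Table 3, marked exception | Red cells, retained | Spinning leaves packed red cells; no storage step is given |
| Banked serum | Section 9 | Serum from clotted blood | No serum tube or clotting step is described |

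The other two collections do not fill the gaps. The 5 mL in section 3.7 is for DNA. The screening sample is clinical only under section 3.3, so it is not a described source for research chemistry or for the bank.

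**Step 2. Direction of the effect on Chemistry**

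This is general laboratory chemistry, not a figure from the documents. Sodium fluoride adds sodium. EDTA binds calcium and magnesium. A potassium salt of EDTA, if used, adds potassium. Both additives can inhibit enzyme assays.

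**Step 3. Illustrative size**

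The protocol gives no additive concentrations and does not name the EDTA salt. The inputs below are assumptions, and results are per litre of whole blood.

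Formula: added mmol/L = (mg/mL × 1000) / molar mass in g/mol.

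Sodium fluoride, 41.99 g/mol, one sodium per molecule:

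- 1 mg/mL: 1000 / 41.99 = 24 mmol/L sodium
- 2.5 mg/mL: 2500 / 41.99 = 60 mmol/L sodium
- 4 mg/mL: 4000 / 41.99 = 95 mmol/L sodium

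Dipotassium EDTA dihydrate, 404.5 g/mol, two potassium per molecule (only if this salt is used):

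- 1.2 mg/mL: 1200 / 404.5 = 3.0 mmol/L EDTA; × 2 = 5.9 mmol/L potassium
- 1.8 mg/mL: 1800 / 404.5 = 4.4 mmol/L EDTA; × 2 = 8.9 mmol/L potassium
- 2.2 mg/mL: 2200 / 404.5 = 5.4 mmol/L EDTA; × 2 = 10.9 mmol/L potassium

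For scale, take usual plasma values, again as assumptions, of about 140 mmol/L sodium, 4 mmol/L potassium and 2.4 mmol/L total calcium. Even the low end adds about 24 / 140 = 17% to sodium, more than doubles potassium, and supplies more EDTA than there is calcium to bind.

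**Step 4. Room for another tube**

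Section 5.1 gives 10 + 10 + 165 + 10 = 195 mL over 12 months, against a cap of 550 mL in 8 weeks. An assumed extra 5 to 10 mL takes the 12-month total to 200 to 205 mL, which is below the 8-week cap even if all of it were drawn within 8 weeks. The 165 mL inpatient figure is not broken down by draw or tube, so the documents do not show whether the extra could be found inside it.

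**The case against.** The best case for the plan is that section 3.3.6 is a short handling paragraph, and tube lists usually sit in a laboratory manual. Table 3 is presented as a list of examples, Chemistry is one undefined word in it, and no aim or hypothesis names chemistry. Electrolytes and liver tests are named only for the screening sample, which this procedure does not govern. *Serum* in section 9 may be loose wording for the plasma that is in fact stored, and stored plasma would still serve many later analyses. Section 1.3 describes the exploratory measures as hypothesis generating and accepts that some may not be collected on everyone.

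Much of this limits the size of the point. It does not remove the mismatch: the text applies one rule to all samples, refers to no manual, marks no exception for Chemistry, and uses a different word for the bank than for the stored fraction.

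A reader might go further and infer three things that the documents do not support.

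- **That all research blood goes by this route and only plasma is kept.** The DNA sample is separate, and the text is silent on the cell fraction; it does not say the cells are discarded.
- **That erythrocyte fatty acids will be entirely missing.** Centrifuging an anticoagulated tube leaves red cells, and Table 3 itself recognises that this measure needs them. What is absent is a storage instruction.
- **That reported chemistry is certain to be wrong by the amounts above.** The panel, the EDTA salt and the concentrations are all unstated.

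**Conclusion.** The point stands as a minor one, in three parts of different strength.

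- **Banked serum:** as written, it has no source. This follows from the text and needs only the fact that EDTA blood does not clot. Whether the remedy is a new tube or a changed word depends on what the sponsor meant.
- **Chemistry:** as written, any electrolyte, mineral or enzyme results in the panel would be invalid. This is conditional on the panel containing such analytes and on its being run on these tubes. The size is not derivable from the documents; the figures above are illustrations under assumed concentrations.
- **Erythrocyte fatty acids:** a storage step is omitted. Collection remains feasible.

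The consequences stop at Exploratory Aim 2 and future banking. The three primary aims, which rest on PET binding potentials, and the sample size of 39 are unaffected.

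**What to change.** In section 3.3.6 and Table 3:

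1. Limit the fluoride/EDTA/aprotinin tube to glucose and the peptide hormones, and add a column to Table 3 naming the tube and matrix for each analyte.
2. Assign Chemistry to a serum or lithium-heparin tube, and list what the panel contains.
3. Reconcile sections 3.3.6 and 9: either add a serum tube for the bank, or change *serum* to *plasma* in section 9 if plasma was intended.
4. Add a step to keep and freeze the red-cell fraction for erythrocyte fatty acids.

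The cost is a revised tube list, one extra processing step, and a small additional volume (assumed 5 to 10 mL), well inside the cap in section 5.1. The blood-volume statement there should be updated to match. If the bank is reworded to plasma, no extra volume is needed for that item. For participants already studied, record which tubes were actually used, and leave out any chemistry results obtained from fluoride/EDTA plasma that the additives affect.

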### 3.3.7 CONTINUOUS GLUCOSE MONITORING SYSTEM

Subjects will wear an FDA-approved continuous glucose monitor (CGM) during their inpatient admission except during MRI procedures. The device will be used to record fluctuations in blood glucose, approximately every 5 minutes. The system consists of a small sensor, transmitter, and hand-held receiver (about the size of a pager). The small sensor, with a small needle attached, will be inserted subcutaneously. The transmitter, which is attached to the sensor, will send the measured glucose to the receiver. The data stored in the receiver will be uploaded to a software for analysis. The sensor is changed once every 7-14 days. The device is calibrated every 12 hours per the manufacturer's product instructions.

CGM readings will not be made available to either nursing staff or participants. Data will be stored in the receiver for later analysis. The device may be calibrated occasionally during the participant's stay, which involves a concurrent finger-stick blood glucose assessment. If during this event a medically actionable blood glucose reading is observed during either fasting or non-fasting conditions (<40 mg/dL or > 200mg/dL), nursing staff are instructed to draw a blood sample for subsequent analysis by DLM and follow standard treatment procedures. In the absence of an observed clinically significant reading, participants complaining of glycemic symptoms will be treated to alleviate symptoms.

